- length of ICU stay
- total admission duration
- Point of care glucose
- venous blood glucose
 - Reduction in patient contact for exclusive purpose of glucose measurement/intervention as compared to q2hr, q4hr, and q6hr POCT glucose checks
 - Enrolled participant's information will be collected from UH Inpatient EMR. This information will include patient name, MRN, DOB, height, weight, gender, ethnicity, type of diabetes and diabetic complications, past medical history of lung disease or cancer, home diabetic medications, in-hospital diabetic medications, history of smoking

and alcohol use, symptoms on admission to the hospital, daily vital signs, blood electrolytes, chemistries including renal and hepatic function, Coronavirus test results, blood cell counts, Hemoglobin A1c, laboratory blood glucose, finger stick glucose, daily insulin requirement, inotropic support, mechanical ventilation status, renal replacement therapy, antibiotic and glucocorticoid use, length of hospital stay, length of ICU admission, imaging modalities used, any adverse events including hypoglycemia and death.

Data Analysis Plan

Each patient's CGM data will be aggregated (e.g., across repeated measures) by Dexcom Clarity App. As a largely descriptive study, standard summary statistics will be computed. Means and standard deviations will be used to summarize the primary outcome (% of time spent in target glucose range of 140-180mg/dL) as well as all other continuous variables. Frequencies and percentages will be used to summarize categorical variables. Poisson regression will be used to determine whether use of CGM reduced the number of times healthcare workers were in contact with COVID-19 patients compared to q2hr, q4hr, and q6hr POCT glucose checks. Univariate and multivariate regression models will be used to explore potential associations between % of time spent in target range and secondary outcomes (e.g., length of stay in the hospital and ICU) while controlling for relevant covariates.

Risks to Research Participants

Sensors may fracture on rare occasions. There is a potential rare risk of sensor breakage and part of it may remain under the skin causing symptoms of infection or inflammation—redness, swelling or pain—at the insertion site. (8) CGM sensor readings may be affected by some of the conditions seen in ICU patients. Volume contraction, renal dialysis, use of vasopressor medications, and metabolic acidosis are examples of physical conditions which may impact sensor readings. In the event that CGM data is discordant to clinical presentation, an alternate glucose reading from fingerstick or lab will be considered. There is also a risk of breach of confidentiality.

Protect the Privacy Interests of Research Participants

Primary identification for recruitment will be provided by the critical care team directly related to the patient's care. These patients will be presented to study personnel for evaluation of inclusion/exclusion criteria confirmation. Once confirmed as a potential participant, an anonymised code will be assigned to that patient's MRN. The anonymised code log sheet will be maintained only in a secured shared drive. Confidentiality of data will be preserved during data transmission via the use of anonymised codes. Participants will be assigned codes based on order and location of enrollment. Identifiable personal information will be stored securely in a locked room at the Department of Endocrinology at UHCMC. Electronic versions will be saved on a desktop computer at University Hospitals using password protected security measures. Data will be accessible only to the Research Team and for audit in a secured shared folder.

Potential Benefit to Research Participants

Benefit for COVID- 19 positive participants

- Increased frequency of glucose monitoring may improve insulin management
- Opportunity for the participants to learn about a device which you may use at home if covered by health insurance.
- Alerts offer improved glycemic variation awareness
- Help to establish effective inpatient methods of CGM use for general diabetic patient admissions
- Potential benefit to healthcare providers by reducing exposure to SARS-CoV-2 virus

Benefits for COVID-19 Negative participants (participants in HFICU)

- Detailed information about glucose patterns available to healthcare team which may improve insulin management.
- Opportunity for the participant to learn about a device which you may use at home if covered by health insurance.
- Alerts offer improved glycemic variation awareness
- Help to establish effective inpatient methods of CGM use for general diabetic patient admissions

Withdrawal of Research Participants

If the subject has serious event related to study

Investigator initiated discontinuation due to participation or equipment concerns

Patient withdrawal of consent

Data collected up until the point of withdrawal may be included in the study

Patient no longer requires glucose monitoring for their care

Alternatives to Participation

Patient may elect to use POCT finger stick glucose measurement 4 to 6 times daily

Patient may use CGM for glucose monitoring without permitting data download

Alternative not to participate

Costs to Research Participants

There is no monetary cost to participants. Cost of study supplies will be funded by the Department of Critical Care Medicine.

Research Participant Compensation

Participants will not receive any monetary compensation for their participation.

Provisions to Monitor the Data to Ensure the Safety of Research Participants

1. Study principal investigator will be responsible for monitoring the data weekly for completeness, accuracy, and adherence to the protocol.
2. There will not be a Data and Safety Monitoring Board or Committee.

Drugs or Devices

Dexcom G6 Personal CGM

Community-Based Participatory Research

This study is in the inpatient setting only so this does not apply to our study.

References

3. A. Wang, W. Zhao, Z. Xu, J. Gu, Timely blood glucose management for the outbreak of 2019 novel coronavirus disease (COVID-19) is urgently needed, *Diabetes Research and Clinical Practice* (2020), doi:<https://doi.org/10.1016/j.diabres.2020.108118>
4. M.A. Hill, C. Mantzoros, and J.R. Sowers, Commentary: COVID-19 in Patients with Diabetes, *Metabolism* (2020).

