 - The ICU staff will record CGM glucose data as displayed on CGM receiver into the “Point of Care” free text flowsheet every 2 hours in the patient’s chart
 - The ICU nursing staff will additionally collect point of care finger glucose readings every 4 hours or as they are scheduled to enter the patient’s room for standard of care in ICU setting.
 - CGM data is saved in the receiver component of the device until downloaded at the end of device use. Download will be saved as an electronic copy with participant’s anonymised ID code as the file name. This file will be stored in the secured shared drive accessible only to study personnel.
- CGM sensor will transmit glucose data in real-time to the receiver placed within a 20 foot distance from the patient on the glass door outside the ICU room. Glucose data can then be viewed in real time by the healthcare team.
- Dexcom will also provide glucose telemetry software which will allow for remote viewing of glucose data from all the patients on CGM.
- The sensor is a single use, disposable device while the transmitter and the display device will be cleaned with alcohol and glucose data downloaded and cleared from the device between participants. This data download is facilitated via Dexcom Clarity App.
- CGM sensors may be worn for a maximum of 10 days at a time throughout the participants’ ICU admission. If a patient’s ICU stay exceeds 10 days, the sensor will be removed by peeling off the adhesive. Nurse will replace it with a new sensor on the patient’s opposite side at the point of an imaginary line of the mid axillary at the level of the umbilicus. The same transmitter is reattached to the new sensor after being clean with alcohol wipe. 2 hour warm up period will repeat and use of CGM will resume as before. Total maximum use for study purposes is 20 days (2 sensor uses).
- Point of care finger glucose readings will be collected every 4 hours. Of these, one fingerstick reading daily will be used for calibration of CGM device at the time prompted by CGM receiver.
- Any CGM glucose readings suggestive of hypoglycemia measuring less than 70 mg/dL, provider/nurse is to confirm with fingerstick glucose reading, then treat according to UH hypoglycemia protocol.
- Any CGM glucose readings suggestive of hyperglycemia measuring greater than 300 mg/dL, care provider is to confirm with fingerstick glucose reading, notify ordering provider then treat according to insulin order placed by care team.

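### The contact-reduction outcome is defined in two ways with no counting rule for its nominal comparator, so it can differ from zero when CGM saves no contacts

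*Combined protocol and SAP*

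**What the plan says.** Lowering staff contact with COVID-19 patients is the second of the two stated objectives, and one of the two hypotheses concerns it. The outcome then appears in two forms.

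- **Data to be collected:** "Reduction in patient contact for exclusive purpose of glucose measurement/intervention as compared to q2hr, q4hr, and q6hr POCT glucose checks".
- **Data Analysis Plan:** "Poisson regression will be used to determine whether use of CGM reduced the number of times healthcare workers were in contact with COVID-19 patients", set against the same three schedules. The exclusive-purpose limit and the mention of interventions are both gone.

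The Study Design section describes no control group, and the heart failure participants also wear CGM.

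Study Procedures keep fingersticks going during CGM. Under glucose data transmission, nursing staff "collect point of care finger glucose readings every 4 hours or as they are scheduled to enter the patient’s room for standard of care". A later bullet says only "Point of care finger glucose readings will be collected every 4 hours". Extra fingersticks follow some CGM readings: "Any CGM glucose readings suggestive of hypoglycemia measuring less than 70 mg/dL, provider/nurse is to confirm with fingerstick glucose reading", and likewise "Any CGM glucose readings suggestive of hyperglycemia measuring greater than 300 mg/dL, care provider is to confirm with fingerstick glucose reading".

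No section says how a check made during an entry for other care is counted on the reference side, or how the reference enters the Poisson model. Room-entry times and purposes are not among the listed record items.

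**The concern.** A before-and-after or between-schedule difference is interpretable only if both sides count the same event. In the data-list wording, the exclusive-purpose limit and the word intervention attach to the observed contacts, while the reference is an unqualified schedule of checks. A fingerstick done during another room entry therefore leaves the observed count while its counterpart stays in the reference. An entry made only to treat enters the observed count and has no counterpart. The first mismatch favours CGM and the second works against it.

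The Poisson sentence adds a third possibility. If it counts every contact, entries for unrelated care are compared with glucose checks alone. The direction of the reported result could then depend on which sentence the analyst follows. This is also the only comparison for which the plan names a model to establish an effect.

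**Working it through.** The documents give no contact rate, effect size, alpha or power for this outcome, so there is no planned figure to reproduce.

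**Inputs from the documents.** Reference schedules: 24/2 = 12, 24/4 = 6 and 24/6 = 4 checks per day. Fingersticks under the protocol: every 4 hours, so 6 per day. COVID-19 participants: 46 − 6 = 40 at the main site and 100 − 6 = 94 study-wide.

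**Inputs assumed, because the documents do not give them.** b, the share of checks done during entries made for other care; i, intervention-only entries per day; o, other-care entries per day.

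**1. Data-list wording, no CGM benefit, matching schedule S.** The observed count is S(1−b) + i and the reference is S, so the score is [S(1−b)+i]/S − 1.

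| S | b | i | Score |
|---|---|---|---|
| any | 0.25 | 0 | −25% |
| any | 0.50 | 0 | −50% |
| 6 | 0.25 | 1 | 5.5/6 − 1 = −8.3% |
| 6 | 0.25 | 2 | 6.5/6 − 1 = +8.3% |
| 6 | 0 | 1 | 7/6 − 1 = +16.7% |

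With i = 0 the false reduction equals b. In general a reduction appears only if Sb > i.

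**2. Schedule mismatch is a separate effect.** Six fingersticks per day with b = 0 and i = 0 give 6/12 − 1 = −50% against q2h, 0% against q4h and 6/4 − 1 = +50% against q6h. Only the q4h comparison isolates the counting rule. Against q6h a reduction needs 6(1−b) + i < 4, that is b > 1/3 + i/6. The only frequency outside the study that the protocol gives, under Alternatives to Participation, is 4 to 6 fingersticks daily, which corresponds to q6h to q4h.

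**3. Poisson sentence read as all contacts.** With no benefit and a matching schedule the score is [o + S(1−b) + i]/S − 1 = (o − Sb + i)/S. If each bundled check falls in its own other-care entry, o is at least Sb and the score cannot be negative. At S = 6, i = 0: o = 6 and b = 0.5 give (6 − 3)/6 = +50%; o = 12 and b = 0.25 give (12 − 1.5)/6 = +175%.

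**4. Effect on a test against q4h, data-list wording.** Assume one-sided 0.025, one CGM-day per patient, independent Poisson counts and i = 0. With a fixed reference of 6 per day, the chance of declaring a reduction is the lower Poisson tail at mean 6(1−b)N. If the reference is entered as Poisson counts, it is Φ{−ln(1−b)/√(1/μ + 1/μ₀) − 1.96}, with μ = 6(1−b)N and μ₀ = 6N.

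| N | b | Fixed reference | Poisson reference |
|---|---|---|---|
| 40 | 0.10 | 0.33 | 0.20 |
| 40 | 0.25 | 0.98 | 0.83 |
| 94 | 0.10 | 0.67 | 0.41 |
| 94 | 0.25 | 1.00 | 0.99 |

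**5. Same rule on both sides.** Let b₀ be the share of reference checks that would have coincided with the patient's other care. Counting only exclusive-purpose checks, the ratio on a matching schedule is S(1−b)/[S(1−b₀)]. With b = b₀ it is 1.00. If CGM allows more bundling, say b = 0.50 against b₀ = 0.25, it is 3/4.5 = 0.67. That is a 33% reduction, where the literal rule reports 50%.

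**The case against.** The documents never say that every scheduled check counts as a contact on the reference side. The exclusive-purpose phrase describes the contact being reduced and could be meant for both sides. This stands: the one-sided count is an inference from an unqualified schedule and the absence of a control group. But if both sides were intended, the protocol gives no way to apply the limit to a hypothetical schedule, so a rule is still needed.

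A reader might go further and infer that a patient with no CGM benefit will always score a reduction. The documents do not support that. Counting interventions on the observed side pushes the other way, the sign depends on whether Sb exceeds i, and neither quantity is given. The Poisson sentence may reverse the bias altogether.

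Bundling may also be part of how CGM saves contact. Staff can read the receiver from outside the room, fingersticks may be taken at planned entries, and the objective is fewer contacts, not fewer fingersticks. This stands too. It is a reason to compare observed bundling with the bundling expected under each schedule, as in step 5, and not to credit all of it to CGM.

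Finally, the study is largely descriptive and its primary outcome is time in target range. That limits the consequence, but a descriptive percentage built on unlike counts misleads in the same way.

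**Conclusion.** The concern holds in a limited form. The plan gives two definitions of the contact outcome and no counting rule for the reference. On the literal data-list wording the score under no benefit is (i − Sb)/S, which may be a false reduction or a false increase. If the Poisson sentence means all contacts, the bias is against CGM. Neither the sign nor the size of a reported reduction could be attributed to CGM. Modest bundling would be enough to matter: under the assumptions of step 4, b = 0.25 with no intervention-only entries gives a false claim against q4h with probability 0.83 to 0.98 in 40 patients.

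The values of b, i and o are assumptions throughout. The plan should correct this because it affects one of two objectives, but it leaves the primary outcome untouched.

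**What to change.** - Use one definition in the data list and the Poisson sentence: glucose-check entries made only for that purpose, per CGM-day. Say where calibration and confirmatory fingersticks fall. The confirmatory ones are checks prompted by CGM and belong in the observed count.
- Apply the same exclusion to the reference. Lay the q2h, q4h and q6h times over each patient's own other-care entries and remove reference checks within a stated window, for example 30 minutes. Repeat with a second window, since the result depends on it.
- Report intervention-only entries separately, outside the difference, because the reference schedules contain none.
- State the person-time offset and how the reference enters the Poisson model.
- Give the all-fingerstick count against 12, 6 and 4 per day only as a supplement. State that the q4h fingerstick schedule largely fixes its ratios at about 0.50, 1.00 and 1.50, and that it does not measure room entries.
- Reconcile the two fingerstick-timing sentences in Study Procedures, since the bundled share depends on them.
- Where entry times are not recorded, report observed contacts descriptively and do not attribute a reduction to CGM.

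The cost is two reworded sentences, a short counting rule, and a record of entry times and purposes, which the listed data items do not include. The reported reduction may be smaller.
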